## Institution-Wide Assurances

This protocol will be conducted fully in keeping with the signed MUSC IRB Principal Investigator Statement of Assurance and Department Chair's Statement of Assurance, when submitted to the IRB as a required component of the MUSC IRB Human Research Review Application.

## 3. Protecting Confidentiality of Participant Data

Certificate of Confidentiality. This study will be conducted in accordance with recently enacted policy regarding the automatic granting of Certificates of Confidentiality to NIH/NINR federally funded research. Participants will be made aware of their rights and the limitations of the release of Protected Health Information during the Informed Consent process.

**Participant Screening and Enrollment.** All data from participants screened for the study will be entered into an electronic study database. Designated research staff will collect, gather, and enter required data (written informed consent, HIPAA Authorization, and demographics) onto study data forms. Screened patients who do not meet study eligibility will have specific screening data entered into the study database. The collected data will be helpful in examining the patient population and feasibility of enrollment criteria and will include reason for exclusion. All dates will be shifted and other Personal Health Information (PHI) will be removed from the study database upon study completion. All data obtained from this study will be used for research purposes only and will comply with Federal HIPAA regulations.

Master Screening and Enrollment Logs will be used by the PM to prepare reports on accrual and attrition for the PI and SMC.

**Case Report Forms (CRF).** All proposed study specific case report forms (source documents) for data collection will be designed by the PI, and, when possible, transferred into electronic Case Report Forms (eCRFs) for use in the study's REDCap database. These study specific eCRFs source documents (study logs for correspondence, compensation and other forms such as pre-eligibility screens) will be coded by the participant's unique study ID# for all data collected including study instruments will be maintained in the participant research record. Completed instruments that require signature on a paper CRF will be scanned and uploaded into the study database to allow for remote electronic safety monitoring as well as maintained on file in accordance with MUSC policies and applicable Federal Regulations for the Conduct of Human Participant Research.

**Binders.** The PC will prepare and maintain a participant-specific CRF binder for each participant containing all non-eCRFs records. A regulatory file will be maintained by the PM to include the IRB-approved Protocol, original Informed Consent documents, HIPAA forms and other required study-related regulatory documents. All paper research records and CRFs will be maintained in a locked file cabinet, stored in a room for research files that is accessible only via a password protected entry system that features security cameras, within the College of Nursing. Access to the research records, study database and PHI's will be restricted to study personnel as approved by the PI and MUSC IRB. As with all studies conducted at MUSC, this study is also eligible for a random audit by MUSC Office of Compliance.

**Data Processing.** This study will use Research Electronic Data Capture (REDCap) for data capture and management. REDCap is a software toolset and workflow methodology for the electronic collection and management of research and clinical trials data. REDCap provides secure, web-based, flexible applications, including real-time validation rules with automated data type and range checks at the time of data entry. Exports are made available for several statistical packages including SPSS, SAS, SUDA, R and Microsoft Excel. The study-specific REDCap electronic database will be designed and developed by the PI, CI, or PC. The provision of REDCap is made available through the South Carolina Clinical & Translational Research (SCTR) Institute at MUSC with NIH Grant awards UL1RR029882 and UL1TR000062.

**Data Security.** Ensuring data security, compliance with 45 CFR 46 and maintaining the integrity of PHI is a top priority. MUSC has Standard Operating Procedures (SOP) to ensure a high level of data security while coordinating electronic and paper data management activities for clinical research trials. The REDCap study database will be hosted in the Biomedical Informatics secure data center at MUSC, a secure environment for data systems and servers on campus, and includes firewall, redundancy, failover capability, backups and extensive security checks. The secure data center has strict access control; only authorized core personnel may access the facility un-escorted. Only authorized users are allowed to connect to the network, and the security of the network is actively monitored. Power and environmental controls have several layers of backups, from interruptible power supplies to alternate and redundant feeds to the local utility company. The REDCap system administrator contributes to the maintenance of institutional disaster recovery and business continuity plans. Load balancers and a highly fault tolerant SAN infrastructure contribute to high availability.

The REDCap system itself has several additional layers of protection including password protection. Access to the data and its security is managed institutionally by sponsored login IDs through a Shibboleth login with an MUSC issued NetID and features a user account management filter that controls who can access the data and to what degree. All personnel must pass an employment background check before being issued an ID. Password complexity, history and expiration standards are implemented at the institutional level. Access to individual REDCap projects and their data is managed by the owner of the project. All transactions are securely delivered to the application using Secure Sockets Layer (SSL – SHA-1 with RSA Encryption; 2048-bits). It is then transmitted internally (behind the firewall) to the database server. All transactions are logged at the server layer (httpd logging), application

layers (REDCap logs activity to a database table), and the database layer, using both query and binary logging. This feature provides audit trails for all changes, queries, data exports and reports. MUSC Information security policies are available at: <https://mainweb-v.musc.edu/security/policy/>

**Data Entry.** Only MUSC IRB approved study personnel that are authorized to have access to the REDCap study database will be granted password access. Study personnel using computers that are connected to the Internet will directly enter data into the remotely housed database. As such, no electronic study data will be stored on hard drives and/or any portable electronic devices. Additionally, all personnel with access to the database will have current University of Miami CITI training in the Conduct of Human Subject Protections, and HIPAA and Information Security trainings that are completed annually. Each participant will be assigned a unique study identifier, all PIs will be masked, and data exports will be limited to the PI or the PC for generating reports and the conduct of statistical data analysis.

**Data Monitoring.** Ongoing quality control procedures will be implemented for data collection, storage and processing. The PM will conduct routine monitoring of the study database and generate a monthly report for review at study team meetings. Standing agenda items for these meetings will include participant recruitment and retention, AE's, protocol deviations, data integrity and overall study conduct. The PI and PC will work to resolve and validate discrepant data. Discrepancies that warrant clarification will be sent to appropriate parties for review and resolution. All data entry and changes made in the study database by authorized study personnel will be automatically logged by REDCap, and provide a transparent visible audit trail for reviewers.

## SECTION C.

### Procedures for Identifying, Reviewing and Reporting Adverse Events

1. **Identifying.** Potential minimum risks identified for participants are outlined in the Protection of Human Participants and will also be outlined in the IRB-approved informed consent document. Additional unknown risks may occur and, if so, will be identified through diligent monitoring by the PI or PC throughout the conduct of this study. During the informed consent process, participants will be advised of the potential risks of participation as identified in the IRB-approved informed consent document and reminded throughout the study that the researchers should be promptly informed about any concerns regarding potential side effects, adverse events, or clinical deterioration. Participants will also be instructed to notify the PI, PC, and/or designee of any suspected adverse events immediately if possible. The PI or PC will maintain an electronic record of all reported adverse events and notify the ISM of all reportable events as they occur. The ISM will have real-time access to the study database to review and monitor all reported SAE that were reported as related to the intervention. Additionally, the BS will generate and provide de-identified cumulative administrative human participant semi-annual safety reports for the ISM and SMC to review.
2. **Reviewing.** Adverse events will be initially be assessed and graded by PM and then reviewed by the members of the SMC according to the following MUSC's IRB Adverse Event Reporting Policy [http://academicdepartments.musc.edu/research/ori/irb/HRPP/HRPP Guide Section 4.7](http://academicdepartments.musc.edu/research/ori/irb/HRPP/HRPP%20Guide%20Section%204.7)
  - **Expected/Anticipated**—Identified in nature, severity, or frequency in the current protocol, informed consent, investigator brochure, or with other current risk information.
  - **Unexpected/Unanticipated**—Not identified in nature, severity, or frequency in the current protocol, informed consent, investigator brochure, or with other current risk information.
  - **More Prevalent**—Occurs more frequently than anticipated or at a higher prevalence than expected.
  - **Serious**—Results in death, is life threatening, requires inpatient hospitalization or prolongs existing hospitalization, results in persistent or significant disability/incapacity, cancer, overdose, or causes a congenital anomaly/birth defect.

The relationship of adverse events to study participation will be determined by the SMC according to the MUSC IRB Adverse Event Reporting Policy:

- **Unrelated**—There is not a reasonable possibility that the adverse event may have been caused by the drug, device or intervention.
- **Possibly Related**—The adverse event may have been caused by the drug, device, or intervention, however there is insufficient information to determine the likelihood of this possibility.
- **Related**—There is a reasonable possibility that the adverse event may have been caused by the drug, device or intervention.

3. **AE and UPIRSOS Reporting.** All reportable AE and unanticipated problems (UPIRSOS) experienced by participants will be reported to the NIH/NINR and MUSC IRB in compliance with their Adverse Event Reporting Policy requirements, using the IRB's password protected on-line secure server adverse event reporting system. Within 24 hours after a reportable AE, SAE or unanticipated problem has been reported by the participant, it will be graded by the PM, forwarded to the study's ISM for review, and then will be submitted by the PI to MUSC IRB. The Institutional Official(s) will review the event and discuss the report with the IRB Chair and the Director of the Office of Research Integrity. After IRB review and acknowledgement, the PI will further review, and the PI or PM will forward a copy of the reportable AE, SAE or unanticipated problem and IRB acknowledgement letter to the NIH/NINR Program Officer through MUSC's OSRP. The activities will be reported to the NIH/NINR within 72hrs. In addition, all cumulative reportable AE, SAE and unanticipated problems included in the ISM reports will be submitted to the NIH/NINR in the PI's Annual Progress Reports.
4. **Examples of Potential Reportable Adverse Events:** In accordance with MUSC IRB Adverse Event Reporting Policy, an AE is reportable if it meets all of the following criteria: 1) is unexpected 2) is related and/or possibly related, and 3) is serious and/or suggests that the research places subjects or others at a greater risk of physical or psychological harm than was previously known or recognized. Additionally, per MUSC's policy all participant deaths, protocol deviations, complaints about the research, and breaches of confidentiality are reportable events. An example of an AE would be new onset chest pain and discomfort (symptom) that could potentially be associated with an acute exacerbation of COPD. The participant's parent reported he/she recently ran out of his/her medication. The steps to be taken include withdrawing the subject from the study and inviting him or her to restart the study after symptoms subside. An example of an SAE would be the death of a participant from acute chest syndrome or stroke, which although would be viewed as unexpected and unrelated to the intervention is nonetheless a reportable serious event. No further steps would be taken except to review, grade and report the event. An example of an unanticipated problem would be the participant trips and falls while retrieving their phone to read a text message reminder. The steps in this case would be to report the event as per the IRB and NINR policy, and to discuss appropriate actions regarding whether the participant should remain in the study with the ISM and SMC. These events and problems will be reported in accordance with the IRB and NIH/NINR policy as noted in Section C.3.

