## **4.0 Study Endpoints**

Study end points include: Successful study completion, participant consent withdrawal, and PI termination due to failure to adhere to the protocol, loss of contact with the patient, and/or unexpected adverse events.

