## 10.0 Study Design / Methods

This is a randomized longitudinal controlled observational study using a mixture of qualitative and quantitative methods. The study will recruit 30 participants and utilize a control group experimental design with dependent pretest and posttest to derive data regarding (1) feasibility and (2) within-participant effect size of the RESP-FIT intervention in terms of satisfaction, use and adherence, technical issues and acceptability, and self-reported symptom severity (dyspnea and fatigue). In addition, information satisfying Exploratory Aim 4 (frequency of physical activity) will be obtained. Patient data (Table 1 below) will be collected at baseline, 6 weeks (post-treatment) and 14 weeks (2 month follow up). This study will enable further development of SAMS using our patient centered iterative design guided by feedback from a convenience sample. When completed, 30 adults (15 in each group) will have used SAMS for 6 weeks. (see Fig. 2 Study Design).

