### Objective Measures:

| Data Collection   | Measures   | Data sources and time points  |
|---|--|---|
| Demographics  | Age, health history, race/ethnicity, rural/urban residence, insurance  | Participant interview and medical records   |
| Clinical Characteristics                                    | FEV1/FVC
Self-reported hospitalizations/exacerbations   | Participant interview and medical records; PFT baseline and at second study visit |
| Maximal Inspiratory & Maximal Expiratory Pressure Generated | MIP and MEP recorded using a calibrated MicroRPM respiratory pressure meter, units in cm H 2 O ; a surrogate parameter for respiratory muscle weakness/strength | Collection and calibration at baseline, and at second study visit.                |
| Physical Activity: Steps                                    | # of steps taken daily (via Fitbit Alta)   | Daily   |
| Physical Activity: Patterns of Active Minutes               | # of minutes active throughout the day (via Fitbit Alta)   | Daily   |
| Sleep   | Hours of Sleep (via Fitbit Alta)   | Daily   |

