
will be continued without increase in the pressure threshold training level. All participants will be managed according to standard treatment protocols used within the MUSC Pulmonary Clinic. Detailed records will be kept pertaining to mortality and morbidity as well as use of inpatient and outpatient hospital facilities, medication use, frequency and duration of disease exacerbations, as well as general response to treatment. All dependent variables will be obtained, for all participants at baseline, mid-intervention (3 weeks post baseline), at intervention end (6 weeks) and 14 weeks (2 months) post baseline.

**Monitoring period:** As per our standard monitoring period with SAMS, participants will receive a daily EMA reminder text. Answering the EMA questions on a smartphone requires 30-45 seconds of time. Probes will occur to not interfere with typical sleep schedule or during school hours. EMA sessions will capture COPD symptoms and emotion/mood over the course of the day. If patients have not filled out an EMA in 3 days, a reminder text will be sent. EMA probe question responses will transfer to RedCap, as TACHL has done with other studies. Data will not be stored on the phone. The participants will be requested to perform video capture of training technique 1 time per week. A reminder will be sent during convenient waking hours if this has not been performed.

**Activity Tracking:** A Fitbit activity tracker will be provided to each participant and comprehensive instruction offered on its use. This activity tracking device is worn on the wrist and only removed for bathing or other activities involving water, as the devices are water-resistant but not waterproof.

**Quantitative and Qualitative Assessments:** Participants will complete quantitative and qualitative assessments of acceptability, feasibility, and performance of the SAM system including:

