One time per week of the study, the patients will be requested to perform video capture of training technique that will be reviewed by our PIs to determine beneficial elements of this video. If applicable, we will also compare return visits to the emergency department and hospital between previous enrollees in the last version of SAMS in a pediatric population. This "on the shelf data" of previous enrollees will be compared to the new enrollees with telehealth visits. 5) Qualitative Key Informant Interviews Qualitative data will be obtained via open-ended interview questions on the acceptability topics above. Interviews will be recorded for transcription and qualitative analyses will be applied using qualitative software program to determine themes in participant responses, which will prompt modifications to the SAMS program. Interviews may be performed over the phone if convenient for the family.

**Participant Compensation:** Participants will receive \$25 for screening, and \$25 at the initial enrollment visit for completion of the initial enrollment assessment and surveys (total of \$50 if enrolled). Additionally,

at the post study evaluation, they will receive up to \$75 for logging into app, wearing their Fitbit, and bringing back the study devices (e.g., Fitbit), completing EMA and surveys, and the brief key informant interview. Final visit compensation will be based on adherence to the study protocol including symptom data entry, EMA reports, telehealth visit, and final visit surveys/KIIs. Each day will be valued at \$2.50 and reimbursement will depend upon adherence to the study protocol including ensuring EMA symptom and training data is available for 5 days manually (for a total of \$12.50/week) for a total of \$75 over the six-week period. Tracking of reimbursement amount during the study will be delivered via the App in a compensation log. \$50 will be reimbursed for completing Visit 2 at Week 6, and another \$50 for completing the two-month follow-up visit. Total up to \$225 = \$75 (EMA and training data \$12.50/week x 6 weeks) + \$50 at Visit 1 + \$50 at Visit 2 + \$50 at Visit 3.

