#### **14.0 Withdrawal of Subjects**

Participants may voluntarily elect to withdraw their consent at any time for any or no given reason while enrolled in the study. The PI may withdraw participants from the study at any time if they decide it is in the participant's best interest, if they do not follow the investigator's instructions, and/or if they fail to maintain contact with the researchers or attend study visits. Withdrawals of participants may also occur if there is a protocol violation or early study closure. All data gathered from withdrawn participants will be used in the analysis plan under an Intention-to-Treat (ITT) model.

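### The chest-pain example in Section C withdraws the participant from the study and invites a restart; pausing training on the original visit clock would fit the ITT plan better

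*Combined protocol and SAP*

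**What the plan says.** Section C, item 4 (under 13.0) works through examples of adverse events. For new chest pain that might accompany an acute COPD exacerbation, it says: "The steps to be taken include withdrawing the subject from the study and inviting him or her to restart the study after symptoms subside".

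Other parts of the plan bear on what follows:

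- **4.0 Study Endpoints** counts among the ways participation ends "PI termination due to failure to adhere to the protocol, loss of contact with the patient, and/or unexpected adverse events".
- **14.0 Withdrawal of Subjects** lets the PI withdraw someone in that person's best interest, and states: "All data gathered from withdrawn participants will be used in the analysis plan under an Intention-to-Treat (ITT) model". It does not mention collecting outcomes after withdrawal, or re-entry.
- **10.0 Study Design / Methods** gives two schedules. The opening paragraph has data at baseline, 6 weeks and 14 weeks. The training-regimen text says: "All dependent variables will be obtained, for all participants at baseline, mid-intervention (3 weeks post baseline), at intervention end (6 weeks) and 14 weeks". It also calls for records of "medication use, frequency and duration of disease exacerbations, as well as general response to treatment".
- **10.0, Randomization and Training Regimen** describes one randomisation, after baseline measures.
- **12.0, Sample Size** specifies an intention-to-treat analysis of within-group pre-to-post change. **12.0, Statistical Analysis** makes adherence one of the primary focuses.

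**The concern.** The example tells staff to remove the person from the study when only the training may need to stop. For a control participant there is no resistance training to stop, so withdrawal mainly ends measurement. The trigger is a change in health, so the outcomes interrupted are those of someone who has just become unwell. An intention-to-treat analysis is meant to keep such people in view.

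The invitation to restart adds a second difficulty. A restarted person could have two baselines, two visit clocks and two partial or full training runs. The plan does not say which of these feeds the change score or the adherence figure. Values taken after recovery on a new clock could stand in for the on-schedule ones, and the same person could be counted as a dropout or as a completer.

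**Working it through.** **1. Reading the sections together.** Withdrawal after an unexpected adverse event ends participation (4.0). Section 14.0 keeps what has already been gathered and provides for nothing further. On-schedule follow-up therefore stops unless the person accepts the restart. That is an inference, but the natural one. Arm: one randomisation (10.0) plus ITT (12.0 and 14.0) implies the arm first assigned. Baseline, clock and run: no section settles these.

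**2. Scheduled visits affected, per person.** These are delayed if the person restarts and lost if not.

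| Withdrawn | Weeks 6, 14 schedule | Weeks 3, 6, 14 schedule |
|---|---|---|
| before week 3 | 2 of 2 | 3 of 3 |
| weeks 3 to 6 | 2 of 2 | 2 of 3 |
| weeks 6 to 14 | 1 of 2 | 1 of 3 |

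**3. Adherence illustration.** Planned training days are 5 × 6 = 30 (10.0). Assume full training to the end of week 3 (15 days), one week off, then full training.

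- Restart, first run counted: 15/30 = 50%.
- Restart, both runs counted: (15 + 30)/(30 + 30) = 75%.
- Restart, second run only: 30/30 = 100%.
- Pause on the original clock, interruption counted against planned days: 25/30 = 83%, a single figure.

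The 50-point spread under restart moves a 15-person arm mean by at most 50/15 = 3.3 points. This uses training days; the percentage that 12.0 defines explicitly is EMA completion, which is not computed here.

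**4. Change score.** Assume the choice of run or baseline alters one person's score by 1 SD, with SDs of 0.5 to 2.0 from 12.0. Shift and half-width are put on the same n.

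- n = 15: shift 0.5/15 = 0.033 to 2.0/15 = 0.133; half-width 1.96 × SD/√15 = 0.253 to 1.012; ratio about 13%.
- n = 25: shift 0.5/25 = 0.020 to 2.0/25 = 0.080; half-width 0.196 to 0.784; ratio about 10%.

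**5. Precision.** The plan's ±0.20 to ±0.78 reproduces as 1.96 × SD/√n with n = 25: 1.96 × 0.5/5 = 0.196 and 1.96 × 2.0/5 = 0.784. With one completer fewer (n = 24): 0.200 and 0.800. Within one arm, assuming 13 falls to 12 and using t quantiles, 0.302–1.209 becomes 0.318–1.271. The plan already allows for 30 − 25 = 5 non-completers, so there may be no loss at all.

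**The case against.** The strongest reply is that this is an illustration, not an operative rule. It sits under a heading of examples, and its mention of a participant's parent, in a trial of adults aged 40 and over, suggests wording carried over from elsewhere. The operative rule is 14.0, where withdrawal is at the PI's discretion. Stopping participation for chest pain is a legitimate safety choice, and the trial is a 30-person pilot that disclaims hypothesis testing. All of this stands, and it sets the severity. It does not remove the point, because no other text gives a specific action for this event and staff may follow it.

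Several stronger readings are tempting, and the documents do not support them:

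- *A reader might infer that the arm is undefined.* One randomisation and ITT largely settle it.
- *That outcomes are lost outright.* A restarter would have later visits, and Section B says reported adverse events are followed to resolution, so the triggering event stays tracked.
- *That the only post-baseline PImax/PEmax is lost.* The Objective Measures table says "Collection and calibration at baseline, and at second study visit", but the training-regimen text schedules all dependent variables at weeks 3, 6 and 14.
- *That ordinary exacerbations lead to withdrawal.* The plan recruits around exacerbation admissions, but it intends to record exacerbations during the study, and nothing says to withdraw people for them.

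**Conclusion.** The point holds as a minor, cheap improvement. The stated step, if followed, takes a person off the outcome schedule for a health-related reason and leaves the baseline, clock and run for analysis unspecified. The undefined restart alone would be only missing detail. What carries the point is the instruction to leave the study when stopping training would do.

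It should not be read as a demonstrated bias. The plan gives no event rate, so frequency may be zero and direction is unknown. For one affected person, under the assumptions above, the effect is up to 3.3 points on an arm's mean adherence, or about 10–13% of a matched half-width if the score changes by 1 SD. The effect on precision is negligible. That outcomes stop at withdrawal is inferred from 4.0 and 14.0 and is not stated outright.

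**What to change.** In Section C, item 4, replace the withdraw-and-restart step with a rule along these lines:

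- Training is paused or stopped as clinically judged, and the participant stays in the study on the original arm, baseline and visit clock.
- Remaining scheduled assessments are collected where this is safe and the participant is willing. Maximal-pressure tests may be deferred.
- Training may resume without a new baseline or randomisation.
- Each person is analysed once, as randomised. Clinically directed interruptions count against planned training days and are also reported separately.
- Withdrawal under 14.0, by the participant or the PI, remains available.

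The cost is an IRB wording amendment, with no added patients or visits. The downside is that some assessments in unwell participants will be deferred, missing or less favourable.
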